Objectives: To test the comparative effectiveness of a conjoint analysis intervention compared to usual care and identify preferred attributes of alternative prostate cancer treatments (including active surveillance) that will aid in designing ways to help patients weigh treatment attributes. We employ values markers, to represent clusters of values for particular aspects of treatments that are valued most by individual patients. Study hypothesis is that conjoint task may have an effect on treatment choice and prostate cancer patients whose treatment is more concordant with their values markers will have improved outcomes. **Study Design:** We propose a two phase study design. In Phase 1, to identify the attributes, we will conduct six focus groups of prostate cancer patients and two focus groups with physicians who treat prostate cancer. Next, we will develop a conjoint task instrument using the attributes identified in focus groups and pilot test it. This task requires the patients to trade-off various treatments by assessing relative importance of particular treatment attributes. Results of Phase 1 will yield a conjoint analysis instrument to identify profiles of treatment values markers, and will be used in Phase 2 to determine common values markers, or profiles of treatment attributes prostate cancer patients value most. Phase 2 consists of a stratified (UPHS, Fox Chase, and PVAMC) randomized controlled trial study of men with localized prostate cancer, aged 45 and randomized to either the conjoint task intervention group or usual care control group, and followed for up to 24 months for objective and subjective outcomes.

Objectives

Overall objectives

Objectives: To test the comparative effectiveness of a conjoint analysis intervention compared to usual care and identify preferred attributes of alternative prostate cancer treatments (including active surveillance) that will aid in designing ways to help patients weigh treatment attributes.

Primary outcome variable(s)

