objective outcomes: cancer recurrence and complications; and subjective outcomes: health related quality of life, psychological well-being, satisfaction with decision and satisfaction with care. **Outcomes Assessment:** As part of Specific Aim 2, following instruments will be used to measure preferences for participation in treatment decision, decision conflict and physician trust for both intervention group and the usual care control group at baseline, immediately after treatment decision, but prior to initiation of treatment. **Control Preferences Scale (CPS):** The CPS assesses the role that patients want to play and perceive playing in treatment decisions [259]. It consists of five sort-cards to assess different roles in decision making, ranging from a fully active to a fully passive role. This survey will be administered at baseline only. **Decision Conflict Scale (DCS):** The DCS is based on a conceptual framework of decision conflict, which is a state of uncertainty about which course of action to take. This scale is well studied in cancer area and has good psychometric properties [260]. We will administer this survey at baseline (before treatment). **Patient Trust-Wake Forest Physician Trust Scale:** This 10-item instrument is

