
phase is critical for determining the salient characteristics of a product or service. Typically, researchers use focus groups that consist of end-users or "experts", to learn from people who have the most experience with the service, but researchers also convene focus groups of people who have little or no experience with a service to learn what may be important for a new user. Focus groups typically are comprised of 6 to 10 participants who do not know one another and who have similar associations to the topic being investigated (i.e., newly diagnosed localized PCa patients). We will make an effort to recruit equal number of surgical and radiation treatment patients and men younger than age 65 and age 65. It is recommended that one conduct at least two focus groups to capture experiences from similar groups of individuals [254-256]. Drs. [name], [name], and [name] each have extensive experience in racial and ethnic disparity research and will carefully construct each focus group. Thus, we will conduct focus groups with good representation from minority and non-minority patients. Of the six patient focus groups, three will be with newly diagnosed patients yet to make treatment decision; and three will be with those who underwent treatment one year ago, providing additional insight into what they wish they had known about the less immediate outcomes and aspects of treatment. In contrast to individual interview, focus group participants relate their experiences and reactions among peers with whom they likely share some common frame of reference. The discussions stimulated in a group setting and listening to others' experiences has the potential to stimulate memories, ideas and experiences relevant to the topic at hand [254-256]. Overarching goal of focus groups is to obtain perspectives of two of the key stakeholders (patients and physicians) about those components or features of PCa care are important to consider in choosing a treatment. The most commonly mentioned and strongly weighted features of treatment across the focus groups will be used to create the conjoint task (to be used in Phase2). If saturation of emerging themes is not reached after six focus groups, we will conduct additional focus groups until saturation occurs. (See Appendix for interview guide that was developed using results of our prior focus group of physicians, discussed in preliminary work). (3) Assigning levels to the attributes. Levels of an attribute may be cardinal (e.g. waiting time, missed work), ordinal (e.g. level of pain) or categorical (e.g. surgery or radiation treatment). Attribute levels will be identified and aligned with the active surveillance (AS) and five active treatment options being studied (RP, RALP, BT, EBRT, PT), reviewed for appropriateness and wording by the study investigators and advisory board members. (4) Developing choice scenarios. Scenarios will describe services, treatment options and outcome configurations for the attributes and level chosen. We will use a fractional factorial design to reduce the number of paired comparisons to the smallest number necessary for efficient estimation of utility weights [49,183,188]. (5) Conjoint task instrument testing. We will pilot test the conjoint task instrument for appropriateness of attributes, levels, language and ease of administration in 20 PCa patients. PHASE 2 Study Population: We will use stratified randomized control trial to study association between value markers and objective (complications and cancer recurrence) and subjective (HRQoL, psychological wellbeing) outcomes across intervention groups, over 24 month period. We will recruit newly diagnosed localized PCa patients from UPHS (Hospital of University of Pennsylvania, Presbyterian Medical Center, and Pennsylvania Hospital), Fox Chase Cancer Center and Philadelphia Veterans Administration Medical Center (PVAMC) and randomize them to conjoint analysis intervention (n=360) or control group (n=360). D.2.1.1 Participants: The sample will consist of 720 newly-diagnosed PCa patients. Inclusion criteria are: (1) treated for PCa at UPHS, Fox Chase Cancer Center or PVAMC; (2) aged 45 years; (3) newly diagnosed with localized PCa and TNM stage T3a; (4) community dwelling; (5) Gleason score 8; (6) low (PSA 10 ng/ml, Gleason 6, clinical stage T1-2a), intermediate (PSA 10 -20 ng/ml, Gleason 7, clinical stage T2b), and high risk (PSA 20, Gleason 8, clinical stage T2c-3a) group [45] and (7) provide informed consent. Exclusion criteria are: (1) Distant, metastatic or un-staged PCa at diagnosis; (2) visited the clinics to obtain second opinion only; (3) moved to another location; (4) unable to communicate in English and (5) cognitive impairment (Mini Mental State Exam or MMSE score < 21). MMSE is a standardized mental status examination widely used for clinical and research purposes [197,198]. D.2.1.2 Recruitment and participant availability: Participants will be recruited from UPHS, PVAMC and Fox Chase Cancer Center's urology and radiation oncology clinics using recruitment protocols that we have successfully used in our prior and ongoing PCa studies. Recruitment will occur in seven steps: 1) determining potential eligibility; 2) obtaining consent from patients urologist/physician; 3) confirming eligibility; 4) screening via phone and interview to assess willingness to participate; 5) obtaining informed consent and HIPAA permissions; 6) baseline assessments; and 7) follow-up assessments. The study and consent form comply with HIPAA Standards for Privacy of Individually Identifiable Health Information. The draft study design and protocol have been approved by the University of Pennsylvania IRB. Future changes will be reviewed and approved prior to implementation. Participant availability: UPHS is a large hospital and physician network in greater Philadelphia area. Approximately 1,600 patients with newly diagnosed PCa are evaluated annually: 40-50% undergo surgery (RP or RALP); 30-40% undergo EBRT

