
among treatment features will be calculated in patient-specific utilities or part-worths associated with the attribute levels in the study. For other outcomes, participants will receive the following surveys via mail within 1-2 weeks after enrollment and prior to treatment initiation: SF-36, EPIC, AUA-SI, regret scale, CES-D, MAX-PC, SWD, PSQ-18, CPS, DCS and trust scale. Demographics, health and family history, clinical covariates and cancer progression data will be collected at 3, 6, 12 and 24 month follow-up. Histological tumor grade Gleason score and PSA and annual Elixhauser comorbidity score [257-258] will be obtained from the Pennsylvania Integrated Clinical and Research Database (PICARD), a UPHS, Fox-Chase Cancer Center electronic database, and PVAMC administrative and patient HER database. Retention and survey administration: During enrollment, importance of active participation will be emphasized. All participants will complete self-administered surveys at baseline within 1-2 weeks after enrollment (prior to treatment initiation) and again 3,6,12 and 24 months post-enrollment (see Appendix for copies of instruments, consent and medical chart review form). Non-respondents will be contacted via telephone after 10 days. In case of non-response due to death, cause of death will be noted and the physician investigators will determine cause of death (PCa or non-PCa related). The PCa conjoint analysis task, DCS, CPS and trust scale will be administered at baseline only, immediately after diagnosis of PCa and before treatment decision. D.2.4 Outcomes Assessment: D.2.4.1 As part of Specific Aim 2, following instruments will be used to measure preferences for participation in treatment decision, decision conflict and physician trust for both intervention group and the usual care control group at baseline, immediately after treatment decision, but prior to initiation of treatment. D.2.4.1.1 Control Preferences Scale (CPS): The CPS assesses the role that patients want to play and perceive playing in treatment decisions [259]. It consists of five sort-cards to assess different roles in decision making, ranging from a fully active to a fully passive role. This survey will be administered at baseline only. D.2.4.1.2 Decision Conflict Scale (DCS): The DCS is based on a conceptual framework of decision conflict, which is a state of uncertainty about which course of action to take. This scale is well studied in cancer area and has good psychometric properties [260]. We will administer this survey at baseline (before treatment). D.2.4.1.3 Patient Trust-Wake Forest Physician Trust Scale: This 10-item instrument is based on a multi-dimensional conceptual model of trust and measures trust in physicians and other health care providers [128-130]. Compared with previous scales, it showed improved internal consistency and variability [129, 131-132, 261]. Trust is measured by the sum of the 10 item scores, ranging from 10 to 50, with a higher score indicating higher trust [129, 131-132, 261]. D.2.4.2 As part of Specific Aim 3, the following outcomes will be measured for both intervention group and the usual care control group after initiation of treatment. D.2.4.2.1 Treatment choice: We will obtain data on primary and secondary treatments received, such as active surveillance, RP, RALP, EBRT, BT or PT via self report and verified from medical chart review. . D.2.4.2.2 Satisfaction with Decision (SWD): The SWD scale measures satisfaction with healthcare decisions. It was developed in the context of postmenopausal hormone-replacement therapy decisions. The six-item scale has excellent reliability (Cronbachs alpha = 0.88) [262]. D.2.4.2.3 Regret scale: Regret represents the unsettling feeling of having made a poor choice of treatment, persistent doubt, and a wish to change one's mind. The Regret scale is defined by three items that assess (1) the mans wish that he could change his mind about the kind of treatment he has received, (2) his feeling that he would be better if he had chosen the other treatment, and (3) whether he is bothered by the fact that other men received very different treatments for their PCa [33]. This scale exhibited good psychometric properties and has been extensively studied [33, 174, 263-265]. D.2.4.3 Following objective and subjective outcome measures will be assessed at baseline and at each post-treatment follow-up period (3,6,12 and 24 months) for intervention group and usual care control group. D.2.4.3.1 Biochemical recurrence: We will define progression of PCa as a change in PCa stage to an advanced stage or PSADT, post treatment [11, 44-45, 55, 160, 203]. We will obtain PSA data at baseline, prior to treatment, and post treatment at three months interval for 18 months. A PSA value of greater than 0.2 ng/ml indicates disease recurrence for surgery patients. For radiation therapy patients, we will adopt the Houston /Phoenix definition of the current PSA nadir + 2 ng/mL, with date of failure determined at call as the biochemical recurrence after radiation therapy [11, 44-45, 55, 160, 203]. Any treatment within six-month of diagnosis will be considered as adjuvant (review by investigators Drs. [name], [name], and [name]). D.2.4.3.2 Medical complications: We will identify complications that occur during either index or subsequent PRINCIPAL INVESTIGATOR (LAST, FIRST, MIDDLE): [name] PCORI Research Plan: Research Strategy 11 hospital admissions within 30 days of treatment [266]. Alibhai, et al. (2005), has grouped complications after RP into seven mutually exclusive categories: cardiac; respiratory; genitourinary; wound or bleeding; vascular; miscellaneous medical; and miscellaneous surgical [266]. Similarly, a list of complications for each treatment type will be developed by literature review and the physician investigators and consultants. D.2.4.3.3 Generic HRQoL- Medical Outcome Study Short Form: HRQoL data will be obtained using the Medical Outcome Study Short Form (SF-36) a multi-

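### Scheduled PSA collection ends 18 months after treatment, but biochemical recurrence is to be assessed at 24 months, and the plan does not say which PSA values support that assessment

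*Combined protocol and SAP*

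**What the plan says.** The section on primary outcome variables names, among the primary outcomes, "objective outcomes: cancer recurrence and complications". D.2.4.3 in the Design section introduces a group of outcomes with the sentence "Following objective and subjective outcome measures will be assessed at baseline and at each post-treatment follow-up period (3,6,12 and 24 months", and biochemical recurrence (D.2.4.3.1) is the first item in that group. The 24-month horizon appears elsewhere too. The Abstract has men "followed for up to 24 months for objective and subjective outcomes", and the Phase 2 study population text, Study duration and Target population all describe recurrence among "outcomes across intervention groups, over 24 month period".

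D.2.4.3.1 then sets the PSA schedule: "We will obtain PSA data at baseline, prior to treatment, and post treatment at three months interval for 18 months". The primary outcome section repeats the same window, "post treatment at three months interval for 18 months".

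Two statements bear on what happens after month 18. D.2.3 and the Procedures section say that "clinical covariates and cancer progression data will be collected at 3, 6, 12 and 24 month follow-up", and that PSA is taken from the sites' electronic clinical databases, with no end date. D.2.4.3.1 also counts a change to an advanced stage as progression.

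The Analysis Plan uses Kaplan-Meier and Cox methods for time to PSA recurrence. For Aim 4 it also measures recurrence by PSA doubling time and fits a mixed model to log PSA. It gives no censoring rule for PSA recurrence.

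**The concern.** The endpoint needs PSA values. D.2.4.3.1 defines recurrence as a PSA above 0.2 ng/ml after surgery and as nadir plus 2 ng/mL after radiation. The Aim 4 doubling-time and log-PSA analyses need the values as well. An abstractor who follows the only stated PSA window would stop at month 18, while the same section asks for recurrence at month 24.

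Two things are at stake. The first is events and precision, on an outcome for which the plan gives no power calculation. The second is the status of men between their last PSA and the end of follow-up. With no censoring rule, a man could be carried as recurrence-free to his 24-month survey with no PSA to show it, and recurrence would then be understated.

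**Working it through.** **The plan's own figure.** There is none to reproduce. The Accrual section bases sample size and power on quality of life and gives no recurrence rate, event count or hazard ratio. The recurrence risks, hazard ratio and treatment delays below are assumptions.

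**Inputs from the plan.** PSA every 3 months for 18 months after treatment (months 3, 6, 9, 12, 15, 18); assessment to 24 months; 720 men. D.2.4.3 calls the follow-up visits post-treatment, whereas the survey text in D.2.3 and in Study duration counts the same months from enrollment.

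**Step 1: the gap if both clocks run from treatment.** 24 − 18 = 6 months, and 6/24 = 25% of follow-up.

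**Step 2: share of events in the gap.** Let F be the assumed 24-month recurrence risk and L = −ln(1 − F)/24 the constant monthly hazard. The share arising after month 18 is 1 − (1 − exp(−18L))/(1 − exp(−24L)).

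| F | Risk by month 18 | Share after month 18 |
|---|---|---|
| 5% | 3.77% | 24.5% |
| 10% | 7.60% | 24.0% |
| 20% | 15.41% | 22.9% |
| 30% | 23.47% | 21.8% |

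**Step 3: precision.** The standard error of a log hazard ratio scales as 1/√(events). Losing 24% of events multiplies it by 1/√0.76 = 1.15.

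**Step 4: illustration with 720 men and F = 10%.** Events are 720 × 0.10 = 72 by month 24 and 720 × 0.0760 = about 55 by month 18. With an assumed hazard ratio of 0.6, equal arms and two-sided 5%, power is Φ(√(d/4) × |ln 0.6| − 1.96), where d is the number of events. This gives 58% at 72 events and 47% at 55. Counting all 720 men is generous, because D.2.4.3.1 gives PSA thresholds only for surgery and radiation. The shares in Step 2 do not depend on this.

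**Step 5: the gap if the 24 months run from enrollment.** Suppose treatment starts t months after enrollment. PSA then ends at month 18 + t and the gap is 6 − t months, out of 24 − t months after treatment. At low risk the share of events lost is close to (6 − t)/(24 − t), and the standard error is multiplied by √((24 − t)/18).

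| t (assumed) | Gap | Share of events lost | Standard error |
|---|---|---|---|
| 0 | 6 months | 6/24 = 25% | +15% |
| 1 | 5 months | 5/23 = 22% | +13% |
| 3 | 3 months | 3/21 = 14% | +8% |
| 6 | 0 | 0 | 0 |

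All of these figures also assume that no PSA value after month 18 is used, so they are upper limits.

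**The case against.** A reader might infer that recurrences after month 18 are never seen, that a 24-month recurrence result cannot be produced, or that the plan rules out later chart values. The documents support none of these. A 24-month collection of progression data is planned, stage change counts as progression, and the database sentence sets no end date for PSA. The 18-month sentence can be read as a three-monthly series that sits alongside the 24-month collection. Nothing says that later values will be ignored.

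The defence can also say that the analysis tolerates the schedule. Kaplan-Meier and Cox methods, censored at the last PSA, remain valid to 18 months. The schedule is the same in both arms, so it does not by itself bias the comparison. The Analysis Plan's emphasis on six and 24 months follows its text on subjective outcomes, and no stated sample size or power figure depends on PSA. The gap also shrinks if follow-up is counted from enrollment.

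All of this stands, and it limits the point without removing it. A stage-change entry at month 24 supplies neither a PSA threshold crossing nor a doubling time. The database sentence names the source of PSA but not the period. Validity to 18 months is not support for a 24-month assessment, and valid censoring depends on a rule that the plan does not state.

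**Conclusion.** The point holds as an unreconciled inconsistency on a listed primary outcome: PSA is scheduled to 18 months after treatment, biochemical recurrence is to be assessed at 24 months, and the end of PSA collection, the time origin and the censoring rule are left open.

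The loss ranges from nothing to about a quarter of events, with up to about 15% on the standard error. It depends on which clock applies, on the delay to treatment and on whether later database values are used. The event shares rest on a constant hazard and assumed risks. The plan also gives no basis for calling recurrence rare, since its background section says that up to 40% of men treated with surgery or radiation may eventually relapse.

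The consequence is mainly lost precision and an unsupported 24-month estimate. A bias reading is tempting but conditional: recurrence would be understated only if men were counted recurrence-free beyond their last PSA, which the plan does not propose but does not exclude. This is a low-cost improvement worth making, not a flaw that undermines the trial.

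**What to change.** Reconcile the 18-month PSA window, in both the primary outcome section and D.2.4.3.1, with the 24-month recurrence outcome. Three sentences would do it:

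- Abstract every PSA value already recorded in the named databases through month 24 for each man.
- State one time origin for PSA, recurrence and the follow-up months, either treatment or enrollment.
- Censor time to PSA recurrence at the last PSA, not at the last survey.

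No additional PSA tests or visits are requested. The cost is up to six more months of chart abstraction per man, from records the study already uses. If abstraction cannot be extended, the censoring rule should still be stated, and PSA-based recurrence should be reported to 18 months only.
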